- a. increase ICP.
- b. diminish cerebral vasoreactive autoregulation as assessed by PrX, ie PrX will turn positive, which means that it will change the state from intact to impaired autoregulation.

The secondary objective is an exploratory analysis of the relationship between ventilator settings and other well defined respiratory, cerebral, and cardiovascular variables. The endpoints are described below.

There is also a third objective, which is described in the sub-project at the end of this document, which is to investigate the role of next of kin in research with ICU patients.

The study will also lead to increased knowledge in this area, which will serve to:

2. Improve ventilator settings for the lungs that at the same time are safe for the perfusion of the brain.
3. Identify important ventilator variables that affect the ICP curve analysis and evaluation of brain compliance and autoregulation, going from basic science to clinical integration.
4. Individualize mechanical ventilation based on airway pressure, transpulmonary pressure and severity of brain injury.
5. Develop the ICM+ monitoring software with incorporation of relevant ventilator signals.

Methodology

Study design

Brain Vent is a single center, blinded, randomized, cross-over clinical trial in a tertiary trauma, neurosurgery center, which will be conducted at the ICU, UNN Tromsø.

Study population

All consecutive admitted tracheally intubated adult patients with ICP monitoring (independent of the study) will be considered for inclusion within 12 hours by the principal investigator through the duration of the study, which is expected to require approximately 18 months to achieve the necessary sample size (see below).

A screening log will be used for participation or non-participation. Reason for non-participation will be recorded.

Inclusion criteria

- Any tracheally intubated or tracheotomized adult patient with ABI with GCS < 10 or Hunt-Hess grade > 3 on controlled ventilation requiring continuous ICP measurement.
- Admission within 24 h after ABI.
- Proxy informed consent from relatives.

Exclusion criteria

- ICP > 22 mmHg before treatment of high ICP
- Acute respiratory failure defined as partial pressure of oxygen/ inspiratory oxygen fraction (PaO₂/FiO₂) ratio < 40 kPa and X ray pathology
- History of pulmonary disease: Chronic respiratory failure diagnosis stage III and IV in the GOLD classification, pulmectomy, lobectomy or restrictive lung disease.

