- Body mass index (BMI) > 35.
- Known right or biventricular cardiac failure with cardiac index < 2,5 L/min/m² or ejection fraction < 40 %.
- Refractory hypovolemia as diagnosed with pulse pressure variation > 12 % with tidal volume 8 ml/predicted bodyweight (intubated on controlled ventilation) or passive leg rise test with > 10 % increase in stroke volume measured by VTI echocardiography or PICCO.
- Medulla lesion that affect the autonomic nervous system.
- Patients who has undergone decompressive craniectomy.

Planned number of participants and statistical analysis

In this study setting, we aim to show that LPV is non-inferior to conventional ventilator setting, with regards to ICP increase or change of PrX > 0.3 (diminished autoregulation).

Sample size calculation is based on the primary outcome and the cross-over study design. Assuming a difference of zero, a standard deviation of 4 mmHg and a non-inferiority margin of 3mmHg, power of 80% and a significance level of 0.025, a total of 28 patients will be included¹⁶. We will recruit 30 patients to Brain Vent to take account of technical issues or dropouts. The non-inferiority margin is chosen to be lower than the minimal clinical important difference of 5 mmHg. It is assumed that there will be no missing data in the period 2 measurements due to the short time interval between the two different interventions. The sample size calculation is done with STATA 15.1 and the main analysis will be done in SPSS.

Descriptive statistics will be presented with mean and standard deviations or median and interquartile range as appropriate for continuous variables. Categorical variables will be presented as proportion of patients in the different categories. Subject level profiles for each group (AB, BA) will be plotted to visualize the results. The hypothesis of non-inferiority will be tested based on the

lower confidence limits of the difference. Period effect, sequence effect and secondary outcomes will be analysed with linear mixed models.

Procedure

Patients will be ventilated with Servo U® ventilators (Maquet, Rastatt, Germany). Treatment will follow local procedures.

Intervention

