Ventilatory settings in detail:

a. Conventional settings- Volume control (VC), inspiratory: expiratory (I:E) ratio 1:2, Tinsp 10 %, PEEP 5 cm H₂O, VT 9 ml/predicted bodyweight, ventilator frequency (Vf) needed to give partial pressure of carbon dioxide (PaCO₂) 4.5-5 kPa, oxygen saturation (SpO₂) > 96. Plateau pressure < 30 cm H₂O

b. Intervention 1- VC, I:E ratio 1:2, Tinsp 10 %, PEEP 5, TV 6 ml/predicted bodyweight, Vf (<30/min) will be increased to the same minute ventilation as in a. Plateau pressure < 30 cm H₂O

c. Intervention 2- VC, I:E ratio 1:2, Tinsp 10 %, PEEP 12, TV 6 ml/PBW, Vf (<30/min) will be increased to the same minute ventilation as in a., SpO₂ > 96. Plateau pressure < 30 cm H₂O

Age (≥ 70 , < 70) and type of damage (TBI or SAB) will be stratified in the two groups in the randomisation.

Observations and outcome measurements during the study:

All primary and secondary outcome measurements will be recorded from minimum 2 hours before to 1 hours after intervention. ICM + will record monitoring signals for 3 h during the start setting for calibration of the PrX signal.

Respiratory component

Respiratory settings and changes will be measured by

- Blood gases: PaO₂/FiO₂ ratio.
- Pressure transducer in esophagus: Esophageal pressure (P_{eso}). Continuously and end-insp/end-exp just.
- Ventilator: Oxygenation index, end-tidal CO₂ (etCO₂), inspiratory oxygen fraction (FiO₂), Peak airway pressure (P_{peak}), P_{plateau}, PEEP, End-expiratory airway pressure (Paw_{Endexp}), Vf, tidal volume inspiratory (VT_{insp}), tidal volume expiratory (VT_{exp}) at each breath, Total PEEP (end expiratory occlusion), from Paw and P_{eso} and hence from P_{tp}.
- Pulse Contour Continuous Cardiac Output (PICCO) thermodilution: Extravascular lung water index (EVLWI) as a determinant of fluids in the lungs.

Cerebral component:

ICP will be measured by:

- Invasive- ICP probe placed intraparenchymal or in the ventricular space
- Non-invasive ICP with transcranial Doppler (TCD) measurement of optic nerve sheath diameter and straight systolic flow velocity or flow velocity of MCA bilaterally.

Intracranial pressure indices, as a measure of compensatory reserve and autoregulation will be assessed by

- Intracranial and arterial pressure waveform analysis with ICM+® - PrX. Compensatory reserve index (RAP) index and mean pulse amplitude (AMP). Slow AMP. See further down for references.

Brain blood perfusion and oxygenation;

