- Brain tissue oxygen tension (PbtO₂). *Only for patients having a clinical indication for CT caput.*
- if clinically indicated.
- TCD measurement of flow velocity in arteria cerebri media.
- Computer tomography (CT) of brain perfusion for assessment of global and local cerebral perfusion during the first 24 h. *Only for patients having a clinical indication for CT caput.*
- Protein S100B is a new outcome prediction tool in brain injury, which is not thoroughly explored²⁷. It will be analysed on admission as part of a description of the severity of ABI.

Cardiovascular component:

Positive pressure ventilation may hamper venous return, which might decrease cardiac index and cerebral blood flow. Therefore, data from the cardiovascular system also will be included.

A PICCO arterial catheter and a central venous catheter will be inserted for continuous measurement of the following intravascular pressures and cardiac index and derived variables by thermodilution once/hour:

- Cardiac output
- Stroke volume
- Arterial blood pressure
- Central venous pressure

- Intrathoracic blood volume index (ITBVI) as determinants of preload.
- The following treatment will be documented:
- Vasopressor dose
 - Inotropic support
- Any fluid transfusion, amount and constitution

Other patient data that will be registered

Background and baseline demographic data of the study population: Sex, Glasgow coma scale before intubation, diagnosis, age, PBW, BMI, type of ICP monitoring, CT Marshall score, extracranial injuries.

In hospital treatment data: Daily fluid administration, duration of invasive and non invasive ventilation, duration and dose of sedation, ICU days, duration of the hospital stay in days from admission to hospital to discharge to home or rehabilitation.

Rationale for choice of monitoring

Cerebral monitoring:

ICP will be measured continuously as part of routine monitoring by invasive ICP probe in the brain. It will also be assessed noninvasively with transcranial Doppler (TCD)²⁸. In the future, non-invasive ICP measurements will most likely be the gold standard. Therefore, it is important to find out if TCD changes reflect changes in ventilator settings as accurate as the invasively measured ICP changes.

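### The plan asks whether non-invasive ICP changes are as accurate as invasive ones but names no agreement or concordance analysis; the only method given for secondary outcomes is a linear mixed model with unstated terms

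*Combined protocol and SAP*

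**What the plan says.** Under Rationale for choice of monitoring (Cerebral monitoring), the protocol expects non-invasive ICP to become the reference method in future and concludes that it is important to "find out if TCD changes reflect changes in ventilator settings as accurate as the invasively measured ICP changes".

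The Cerebral component of the outcome list gives two ways of measuring ICP: "Invasive- ICP probe placed intraparenchymal or in the ventricular space" and "Non-invasive ICP with transcranial Doppler (TCD) measurement of optic nerve sheath diameter and straight systolic flow velocity or flow velocity of MCA bilaterally".

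Under Study objectives, the secondary objective reads: "The secondary objective is an exploratory analysis of the relationship between ventilator settings and other well defined respiratory, cerebral, and cardiovascular variables". Comparing the two ICP methods is not listed there.

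The analysis text is in Planned number of participants and statistical analysis. Beyond descriptive statistics, individual profile plots and the non-inferiority test, it says: "Period effect, sequence effect and secondary outcomes will be analysed with linear mixed models". It states no fixed effects, random effects or covariance structure for the secondary outcomes. The documents contain no bias estimate, limits of agreement, concordance measure, rule for pairing TCD readings with invasive ICP, or conversion formula to mmHg.

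**The concern.** Whether one method tracks a change as accurately as another depends on what the two show in the same patient at the same change of setting. A model of the setting effect, fitted to the non-invasive measure alone, estimates its average shift. Two methods can shift equally on average and still disagree widely within patients.

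The plan's design assumption sharpens this. The sample size takes the true ICP difference as zero. If that is right, invasive ICP shows almost no mean shift, and so would a non-invasive measure that carried no information about ICP. Matching averages, or two non-significant setting effects, are then what a useless method would also produce.

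Others may act on the answer. The Cooperation section foresees the non-invasive technique being useful in other hospitals and easing discussion of patients between remote hospitals and the neurosurgeon.

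**Working it through.** **Inputs from the plan.** The sample size rests on "Assuming a difference of zero, a standard deviation of 4 mmHg and a non-inferiority margin of 3mmHg", with "power of 80% and a significance level of 0.025, a total of 28 patients will be included"; 30 are to be recruited. Table 1 gives each patient two interventions, each preceded by a conventional segment, so there are up to two paired changes per patient.

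**Inputs assumed.** The documents give no SD for any non-invasive measure and none for a between-method difference. I take the same mean change and the same SD of change, s, for both methods, and vary the within-patient correlation of changes, ρ.

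**Step 1: the plan's own figure.** N = 2 × (1.96 + 0.842)² × 4² / 3² = 2 × 7.85 × 16/9 = 27.9, so 28. The stated total reproduces when 4 mmHg is the within-patient SD. If 4 mmHg were the SD of the paired difference, N would be 7.85 × 16/9 = 13.95, so 14. On the reading that reproduces 28, the SD of a change between two segments is 4 × √2 = 5.7 mmHg. I therefore show both s = 4 and s = 5.7.

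**Step 2: limits of agreement for the change.** The between-method difference in change has SD s × √(2(1 − ρ)), so the 95% limits around the bias are ±1.96 × s × √(2(1 − ρ)).

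| ρ | s = 4 mmHg | s = 5.7 mmHg (4√2) |
|---|---|---|
| 0 | ±11.1 | ±15.7 |
| 0.5 | ±7.8 | ±11.1 |
| 0.9 | ±3.5 | ±5.0 |

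**Step 3: what a separate setting-and-period model sees.** Simulation: 30 patients, 2,000 repetitions, assumed mean change 2 mmHg, s = 4 mmHg, model fitted to each method separately.

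| ρ | Invasive: estimate (SE) | Non-invasive: estimate (SE) | Limits of agreement |
|---|---|---|---|
| 0.95 | 2.02 (0.72) | 2.02 (0.72) | ±2.5 |
| 0.5 | 2.01 (0.73) | 1.97 (0.72) | ±7.8 |
| 0 | 1.98 (0.72) | 2.00 (0.72) | ±11.0 |

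The setting effects and standard errors are the same in every row apart from simulation noise. Only the limits differ.

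**Step 4: can a mixed model do it?** A mixed model with a method term and a patient effect, fitted jointly to both methods in 2,000 simulated patients with one change each, gave limits of ±2.5 (direct calculation ±2.5) at ρ = 0.95 and ±10.9 (direct ±10.9) at ρ = 0. It can, provided the two methods are modelled together.

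**Step 5: precision.** With one paired change per patient, the 95% confidence interval for each limit has half-width t × √(1/n + 1.96²/(2(n − 1))) in units of the SD of the between-method difference. At n = 30 this is 2.045 × √(0.0333 + 0.0662) = 0.65; at n = 28 it is 0.67. For assumed SDs of 2, 4 and 6 mmHg the half-width at n = 30 is about 1.3, 2.6 and 3.9 mmHg.

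**The case against.** - **The model terms are not in the text.** This stands. A per-outcome setting effect is an inference from the wording of the secondary objective and from the cross-over comparison of interventions. It is the natural reading, but the plan does not commit to it.
- **Mixed models can measure agreement.** This stands too (step 4). A reader might infer that the plan has chosen a class of model that cannot address the question. The documents do not support that: the gap is an unspecified model and no stated joint analysis, not the use of mixed models.
- **The question is rationale, not an objective.** True. It sits in the monitoring rationale of an exploratory study, with no endpoint or threshold attached. That limits its weight, but a question the protocol calls important still needs an analysis that can answer it.
- **The sentence could mean responsiveness to settings.** A setting effect does bear on that. But the sentence makes invasive ICP changes the comparator for accuracy, and separate mean shifts do not settle that comparison.
- **The figures are hypothetical, and sheath diameter and flow velocity are not in mmHg.** Both stand. The limits illustrate size only, and mmHg limits apply only after a conversion that the documents do not give.
- **Nowhere does the plan say it will report equal mean shifts as equal accuracy.** Correct. That is a risk left open, not a stated intention.

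**Conclusion.** The concern holds as a gap in the analysis plan: a method-comparison question is posed, both measures are listed, and no agreement or concordance-of-change analysis is specified. If the mixed model is fitted to each outcome separately, its setting effect is the same whether the limits of agreement are about ±11 or ±3.5 mmHg (s = 4), or about ±15.7 or ±5.0 mmHg (s = 5.7). These figures assume equal means and equal SDs of change for the two methods and correlations of 0 to 0.9, none of which the plan gives. The primary non-inferiority analysis and the total of 28 are untouched.

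A reader might also infer that the plan's 3 mmHg and 5 mmHg are limits the non-invasive method must meet. They are not. The first is a non-inferiority margin for a mean ICP difference and the second a minimal important difference for ICP. Neither is a criterion for agreement within individual patients, so they can be shown as context only.

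**What to change.** Keep the linear mixed model for setting effects and state its terms. Add a prespecified method-comparison analysis of non-invasive against invasive ICP:

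- Analyse paired changes, each intervention minus its preceding conventional segment, and state when TCD readings are taken and how they are matched to invasive ICP.
- Where the non-invasive measure is converted to mmHg, fix the formula before analysis. Report mean bias and 95% limits of agreement with confidence intervals, allowing for two changes per patient, for example by a joint mixed model with method and patient terms.
- For measures left in their own units (sheath diameter, flow velocity), report within-patient concordance or correlation of change.
- State that equal accuracy will not be concluded from similar mean shifts or from non-significant setting effects.

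The cost is some wording and a short extra analysis. The limits will be imprecise at 30 patients (step 5). The analysis also depends on TCD readings being available in each segment: the plan gives a general recording window but no TCD frequency, so this should be confirmed before promising that no further measurements are needed.
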